5.0 Special Considerations

5.1 Health Insurance Portability and Accountability Act (HIPAA) N/A

5.2 Family Educational Rights and Privacy Act (FERPA) N/A

We will review educational records from the parents or legally acceptable representative, when available. We will not be requesting any records from the participant's school. These records may include individual educational plans or psychological evaluations. We will only record results of recent psychological testing in RedCap using the patient identifier. We will not copy / keep any of these records.

5.3 Code of Federal Regulations Title 45 Part 46 (Vulnerable Populations)

A. Special Populations

- This study includes minors with developmental disabilities, however, does not involve greater than Minimal Risk to participants. tDCS has been used in research studies with both children and adults as well as with individuals with and without cognitive disabilities. This procedure presents the prospect of direct benefit for the individual participant compared to the minimal risk which will be monitored by the research team throughout the study. For example, it has been shown that children in school or ABA programs can plateau at some point and have difficulty learning despite intensive one on one teaching using ABA. tDCS has been shown to improve learning in children with autism.
- Our team has extensive clinical experience with tDCS and has not encountered any difficulty with the tolerability of the treatment.
- Participants will be exposed to the tDCS treatment system before randomization and families will be trained on how to enable the participant to feel comfortable with the procedure. Participants can withdraw from the study at any time.
- ➤ The participants will be between the ages of 5-12 years old. For those participants with a mental age > 7, assent will be obtained for the study as well as parent consent. Participants will be explained about the research in non-scientific terms compatible with his/her understanding.

5.4 General Data Protection Regulation (GDPR) N/A5.5 NJ Access to Medical Research Act (Surrogate Consent) N/A

6.0 Data Management Plan

6.1 Data Analysis

Analysis of the data in this study will follow the approach described in Wellek, S., and M. Blettner (2012). The following steps are required:

1. Baseline analysis to check the assumption of negligible carryover effects. This test has to be performed like an ordinary unpaired t-test

- .2. Test for differences between treatment effects. Formally, this test is carried out according to the same scheme as the pre-test. The crucial difference is that the customary formula for the unpaired t-test are now applied to the within-subject differences
- 3. Significance decisions: The significance of the difference between two treatments (tDCS and sham) is determined as well as the significance of carryover effects (step 1).

These steps are described in more detail below.

Baseline Analysis

For descriptive purposes, summary statistics of the demographic and outcome variables will be calculated. To ensure pre-stimulation (i.e., baseline) equivalence between participants assigned to the two treatment orders (i.e., sham-active vs. active-sham), the outcome measures obtained during the first baseline period (first baseline assessment session) between these groups will be compared using independent *t*-test comparisons. The primary dependent variable will be the BRIEF; fixed factors will be the treatment order (active-sham versus sham-active), and treatment condition (active and sham condition) and the secondary dependent variable will be the PDDBI. We note that, as described previously, the BRIEF will be used to assess executive functioning and the PDDBI is used to differentiate ASD from other conditions as well as to assesses the effectiveness of treatments in terms of Response to Interventions (RTI). The goal of this baseline assessment is to establish the equivalence of the two groups prior to intervention on the basis of the two outcome assessments.

In addition to summary statistics for the baseline assessments, nonlinear EEG features will be computed before testing for all subjects. Machine learning classifiers will be used to demonstrate that the two groups are equivalent and cannot be distinguished based on nonlinear EEG analysis (see [name] et al., 2018).

Hypothesis Testing

As described briefly above, an unpaired t-test is applied to the within-subject differences for the outcomes of interest. We note that two summary outcome scores can be used (BRIEF and PDDBI), as well as for subscores. Because the subscores and the total scores are not independent, a Bonferroni correction is likely too strict and not warranted. Total scores and subcategory scores on each assessment will be tested for significant changes over time. The dependent or outcomes to be measured for within-subject differences within each group assignment (or treatment order: active-sham versus sham-active), treatment condition (active versus sham), and time (baseline and 4-week follow-up) will be the dependent variables. Independent variables will be group assignment, treatment condition, and time. The differences over time in either active or sham condition will be carried out using independent measures ANOVA. For all analyses, *P* values less than 0.05 will be considered statistically significant. Analyses were completed using standard R software.

EEG as a Biomarker for Treatment Outcome

The signal or time series from each sensor will be decomposed into multiple frequency bands using a wavelet transform (Walker, 2008). We note that the Haar wavelet transform yields a multiscale decomposition that is mathematically equivalent to the coarse-graining procedure first introduced by (Costa, Goldberger, & Peng, 2005) for multiscale entropy analysis of biological signals. The use of wavelets for multiscale signal decomposition and relationship of scale to traditional EEG frequency bands is discussed in ([name] et al., 2018). Using the wavelet transform, each sensor signal will be decomposed into power-of-two frequency bands that are approximately equal to the commonly used definitions of delta, theta, alpha, beta, gamma, and gamma+ bands used for EEG analysis. The specific software used for the wavelet transform is publicly available, along with instructions and python code, at: https://pywavelets.readthedocs.io.

Several nonlinear values will be computed on multiple scales for every sensor, including sample entropy, Lyapunov exponents, detrended fluctuation analysis (DFA), and correlation dimension (CD). These will be computed on multiple scales using publicly available software "Nonlinear measures for dynamical systems" or nolds, version 0.3.2, which can be downloaded from (https://pypi.python.org/pypi/nolds).

Nonlinear values derived from Recurrence Quantitative Analysis (RQA) will be computed. RQA is an empirical approach to analyzing time series data that is in principle capable of characterizing all the essential dynamics of a complex system. It has been found to be useful for analyzing "real-world, noisy, high dimensional data" (Webber & Zbilut, 2005). Software for computing recurrence plot statistics is publicly available python package pyRQA 0.1.0 (Marwan, 2012). At least seven of the most commonly used recurrence plot values (RR, DET, LAM, L_max, L_entr, L_mean, and TT) will be computed and used in this study. These values have proven to be potential biomarkers for autism ([name] et al., 2018) and absence epilepsy ([name] et al., 2017) in our previous studies.

EEG analysis will first determine significant group differences between actual and sham tDCS for each of the nonlinear signal features computed. We hypothesize that significant changes will be observed in the nonlinear signal features. A Bonferroni correction will be required for the set of nonlinear measures. In addition to feature comparisons, regression models will be computed using the nonlinear EEG features as input variables and the change in assessment scores as output. Linear regression and machine learning regression models will be used.

Taken together, these analyses will provide the information necessary to determine if tDCS significantly improves the efficacy of behavioral therapy for improving cognitive function in children with ASD. In addition, the usefulness of EEG as a tool for measuring the changes in brain function due to tDCS augmented behavioral therapy will be determined.

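### The only carryover check the plan details is a t-test on pre-stimulation (week 4) scores, which cannot detect carryover; the baseline equivalence claims are also unsupported

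*Combined protocol and SAP*

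**What the plan says.** Section 6.1 (Data Analysis) follows a cited crossover paper and lists three steps. Step 1 is a "Baseline analysis to check the assumption of negligible carryover effects. This test has to be performed like an ordinary unpaired t-test". Step 2 tests the treatment effect with the same t-test formula on within-subject differences. In step 3 the significance of the treatment difference "is determined as well as the significance of carryover effects (step 1", so carryover is one of two formal decisions. Step 1 does not name the variable to be tested.

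The section then says "These steps are described in more detail below". The only matching text is the Baseline Analysis subsection, where "the outcome measures obtained during the first baseline period (first baseline assessment session) between these groups will be compared" by independent t-tests. It describes these data as pre-stimulation and adds: "The goal of this baseline assessment is to establish the equivalence of the two groups prior to intervention". For EEG it says: "Machine learning classifiers will be used to demonstrate that the two groups are equivalent". It gives no equivalence margin, confidence-interval rule or accuracy threshold.

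The Research Timeline and Table 2 (section 1.3) put Baseline 1 at week 4, the first stimulation period in weeks 5-8, washout in weeks 9-12 with Baseline 2 at the end of week 12, and the second period in weeks 13-16. BRIEF, PDDBI and EEG are scheduled at weeks 4, 8, 12, 16 and 20. No carryover analysis is assigned to week 12.

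**The concern.** Carryover in this design is an effect of first-period active stimulation that is still present when the second period is measured. Scores taken before anyone is stimulated cannot reflect it. Either the carryover variable is unspecified, or, taking the plan's own detail as the specification, the test uses data that cannot answer the question. On either reading, step 3 would report a carryover decision with nothing behind it.

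This matters because the proposed mechanism in section 1.1 is synapse formation and learning, which makes some lasting effect plausible, although the 4-week washout separates the periods. Residual carryover can bias the active-versus-sham estimate, and section 6.1 closes by saying that the analyses will "determine if tDCS significantly improves the efficacy of behavioral therapy".

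A separate, lesser point is that a non-significant t-test, or a classifier that fails to separate about 10 to 12 children per order, does not show that the groups are equivalent. This is an unsupported statement; it does not bias the within-subject treatment contrast.

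**Working it through.** **Inputs from the plan.** 24 enrolled and 20 to complete (sections 1.3 and 4.3), so 12 or 10 per order; significance at 0.05 (section 6.1), taken as two-sided. The plan gives no effect size, SD, correlation or margin, so there is no figure of its own to reproduce. Effects below are in SD units, and effect size, correlations and persistence are assumptions.

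**1. Does the week-4 test respond to carryover?** Both orders are untreated at week 4, so under randomization the expected difference is zero whatever happens later, and the test rejects at its 5% level. A simulation of 40,000 trials (effect 0.8 SD, within-child correlation 0.6, carryover only from active into period 2) gave:

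| Unpaired t-test at | Half the effect remains | All remains |
|---|---|---|
| Week 12, 10 per order | 13% reject | 40% reject |
| Week 12, 12 per order | 15% | 47% |

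The week-4 test stayed at 4.6% to 5.2% from no carryover to full carryover. Its flat rate does not depend on the assumptions.

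**2. What would undetected carryover do?** Let τ be the true effect, and L12 and L16 the carried-over effect at weeks 12 and 16 in the active-first order.

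- End-of-phase scores (week 8 v week 16): ½[(τ - L16) + τ] = τ - L16/2.
- Change from each period's own baseline: ½[(τ - (L16 - L12)) + τ] = τ + (L12 - L16)/2.

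| Share of τ left at week 12, week 16 | Bias, end-of-phase | Bias, own-baseline change | Estimates if τ = 0.80 SD |
|---|---|---|---|
| 0, 0 | 0 | 0 | 0.80, 0.80 |
| 50%, 25% | -12.5% | +12.5% | 0.70, 0.90 |
| 50%, 50% | -25% | 0 | 0.60, 0.80 |
| 100%, 100% | -50% | 0 | 0.40, 0.80 |
| 50%, 0 | 0 | +25% | 0.80, 1.00 |

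The simulation with 10 per order reproduced the second, third and fourth rows. Week 16 is 8 weeks after period-1 stimulation ends, so the larger persistence values are upper cases. The plan does not fix the contrast: "time (baseline and 4-week follow-up) will be the dependent variables" fits more than one reading.

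**3. Can week 12 settle the matter?** By the non-central t distribution, the difference detectable with 80% power is 1.32 SD (10 per order) or 1.20 SD (12 per order). Adjusting for week 4 multiplies the SD by √(1 - r²) and costs one degree of freedom. With a week-4 to week-12 correlation r of 0.5 to 0.8, the detectable difference becomes 1.15 to 0.80 SD (10 per order) or 1.04 to 0.72 SD (12 per order). The adjusted 95% CI half-width with 10 per order is t(0.975; 17) × √(1 - r²) × √(2/10): 2.11 × 0.866 × 0.447 = 0.82 SD at r = 0.5, and 2.11 × 0.6 × 0.447 = 0.57 SD at r = 0.8. Week 12 is informative as an estimate, but not as a pass/fail test.

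**4. Equivalence.** The unpaired t-test has 18.5% power (10 per order) or about 21.5% (12 per order) for a true 0.5 SD baseline difference, so it misses one in about 82% or 78% of trials. A formal equivalence test with an assumed 0.5 SD margin would need 2 × [(1.645 + 1.282)/0.5]² = 68.5, so 69 per order, for 80% power.

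**The case against.** **The intended variable may be different.** The Baseline Analysis subsection never mentions carryover; linking it to step 1 rests on the shared label and the promise of detail. The plan defers to a published crossover method, and step 2's contrast with within-subject differences suggests another variable was meant for step 1. That may be so, but no other variable is named, and the detail supplied points to week 4. The finding is about the plan as written, not the cited method.

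**The order factor could respond to carryover.** Section 6.1 lists treatment order as a factor. On the sum of the two end-of-phase scores, the between-order difference is (τ + L16) - τ = L16. This is true, but the plan neither calls it a carryover test nor connects it to step 3. It is also weak: with 10 per order and 0.8 SD carryover, a t-test on that sum rejected in only about 15% to 17% of simulated trials (correlation 0.8 to 0.5).

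**The treatment test is unaffected, and this is a pilot.** Step 2 is not conditional on step 1, and any bias exists whichever check is used. This stands: the direct harm is an uninformative statement about carryover. But that statement is a listed result, and the plan also intends a conclusion on efficacy.

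**The bias figures depend on the contrast.** This also stands. Own-baseline change has no bias under constant carryover. A further reading, outcome four weeks after treatment (weeks 12 and 20), is not covered by the formulas; under it the week-12 difference is partly a period-1 outcome.

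**Conclusion.** The concern holds. As described, the carryover check uses data that precede all stimulation and rejects about 5% of the time whatever the carryover, so step 3's decision would be empty. That conclusion follows from the timing of the assessments and needs only randomization. The consequence for the treatment estimate is conditional: for end-of-phase scores 0 to -50% of the effect as persistence at week 16 goes from 0 to 100%; for own-baseline change, 0 to +25% over the patterns shown. The documents do not say how much carryover to expect, and none may remain after washout. The defect should be corrected before analysis, because a required step cannot do its stated job. The equivalence wording is a secondary correction with no effect on the treatment contrast.

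**What to change.** In section 6.1:

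- State the data and contrast used for carryover. Remove the week-4 comparison from that role, keep it as a descriptive summary of balance, and delete the equivalence claims for the t-test and the classifier.
- Report the between-order difference at Baseline 2 (week 12), adjusted for week 4, with a 95% CI, as a description of residual effect. State that its p-value will not select the analysis.
- Prespecify one sensitivity analysis: the first-period comparison, week 8 adjusted for week 4, which is free of carryover.
- Name the within-subject difference that is the treatment contrast: end-of-phase, change from each period's own baseline, or, if intended, the score four weeks after treatment. In the last case, say how week 12 will be interpreted.

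The cost is wording and two extra analyses; no new assessments are needed. There are three downsides. The first-period analysis is less precise: with 10 per order its standard error is √(1 - r²) × √(2/n), against ½√(4(1 - r)/n) for the end-of-phase crossover contrast. That is 0.387 v 0.224 at r = 0.5 and 0.268 v 0.141 at r = 0.8, or 1.7 to 1.9 times larger. Against own-baseline change, with standard error √(2(1 - r)/n), the ratio is about 1.2 to 1.3. The week-12 interval will be wide, about ±0.57 to ±0.82 SD. And the report can no longer say that carryover was tested and excluded.

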1.3 Research Design and Methods

A. Research Procedures

Study Subjects

Participants will include school-aged children with ASD between the ages 5-12. We selected this age group because a diagnosis is typically made by the age of 5. This age group also allows us to profit from neuroplasticity while avoiding potential variables related to children undergoing puberty. This age group is also likely to be enrolled in intensive ABA programs aimed at executive functioning and social communication intervention. Based on the gender distribution of ASD in the population, we expect that our group will be approximately 75% male. Participants will be recruited from the local New Jersey community, from ABA schools and ABA agencies.

Experimental Design

The study will use a randomized double-blind controlled placebo (sham tDCS) crossover design. The study will involve 5 total months of participation. Participants will be randomized into two groups using a random number generator. They will receive either:

- A) 20 active tDCS stimulation followed by 20 sham stimulation: or
- B) 20 sham stimulation followed by 20 active tDCS stimulation.

Randomization & Blinding

We anticipate recruiting 24 participants in anticipation of 4 subjects dropping out. We will use SAS programming to generate a randomization schedule with a block length of 6 and four blocks. Participants will enter the randomization schedule after consent is obtained and they are assigned a study ID.

002	2	Sham	tDCS
003	2	Sham	tDCS
004	1	tDCS	Sham
005	2	Sham	tDCS
006	1	tDCS	Sham

Block 1 example- there will be four blocks = 24 participants recruited.

[figure not shown]
Subjects 21-24 (to account for drop outs) will receive randomization order of the subject they are replacing but will receive a new study ID. For example if the subject with study ID 004 drops out then subject with study ID0021 will receive randomization schedule 1.

[name] will utilize the generated randomization schedule to provide active tDCS and sham stimulation codes that will be entered into the tDCS device (by the parent) prior to each session. These numeric codes will be random numbers and not distinct to the study group assignment, protecting the blind. Because of her role, [name] will remain unblinded and will not be involved in any assessments. All other study staff, including Drs. [name], [name], and [name], will remain blind. Parents, participants, and ABA providers will also remain blind.

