4.2 Secondary Subjects N/A

4.3 Number of Subjects

A. Total Number of Subjects

- Total number of subjects screened = 30
- Total Number of Subjects eligible: 24 participants eligible and enrolled
- Required Number of Subjects to Complete Research: 20 participants to complete.

B. Total Number of Subjects If Multicenter Study N/A

C. Feasibility

Given the number of participants receiving home-based ABA therapy in NJ, we do not anticipate difficulty with recruitment.

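### Baseline t-tests and EEG classifiers are meant to show that the two order groups are equivalent, but with about 12 children per order and no equivalence criterion they cannot.

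*Combined protocol and SAP*

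**What the plan says.** The Baseline Analysis part of section 6.1 opens with its aim: "To ensure pre-stimulation (i.e., baseline) equivalence between participants assigned to the two treatment orders". The method is a test for a difference: "the outcome measures obtained during the first baseline period (first baseline assessment session) between these groups will be compared using independent" t-tests, with BRIEF as the primary and PDDBI as the secondary variable. The paragraph closes by restating the aim: "The goal of this baseline assessment is to establish the equivalence of the two groups prior to intervention". The next paragraph extends it to EEG: "Machine learning classifiers will be used to demonstrate that the two groups are equivalent and cannot be distinguished based on nonlinear EEG analysis".

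The only decision criterion in section 6.1 is the general one for all analyses, that P "values less than 0.05 will be considered statistically significant". The section gives no equivalence margin for BRIEF, PDDBI or EEG, no equivalence test, no accuracy threshold for the classifiers, and no action to follow either result.

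On numbers, section 1.3 states "We anticipate recruiting 24 participants in anticipation of 4 subjects dropping out" and that SAS will be used to "generate a randomization schedule with a block length of 6 and four blocks". Section 4.3 states "Required Number of Subjects to Complete Research: 20 participants to complete". Section 1.5 justifies the size only by calling the study a pilot.

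**The concern.** A t-test of no difference can give evidence that two groups differ. It cannot, by coming out non-significant, give evidence that they are alike. That needs a margin stated in advance and an interval narrow enough to lie inside it. The plan has no margin, and the sample is too small to give a narrow interval. The classifier step has the same fault: a classifier that does not separate 24 children may reflect similar groups or simply too few children.

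The question is also poorly chosen. The order is randomised, so under sound allocation any baseline difference is due to chance, and a p-value for it tests something already known. What matters is how large the realised imbalance is, and that is a matter for description.

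At stake is a statement in the report that the two order groups were shown to be equivalent on executive function, autism behaviour and EEG. The pilot is meant to support a larger trial, so the statement may be carried forward.

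**Working it through.** **Inputs from the documents**
- 24 children randomised and 20 to complete (sections 1.3 and 4.3). The arithmetic agrees: 4 blocks × 6 = 24, and 20 + 4 dropouts = 24.
- The example block in section 1.3 has three children in each order, so allocation is 1:1, giving about 12 per order, or 10 among completers. Twelve is the natural figure for a baseline comparison, because the first baseline precedes treatment.
- Significance level 0.05 (section 6.1).

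**Assumptions**
- Two-sided tests (the plan does not say) and normal data.
- Imbalance in SD units, since no SD or margin is given. I use 0.5 SD as a reference imbalance and margins of 0.5 to 1.5 SD.

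The plan states no power or equivalence figure, so there is none to reproduce beyond the sample size.

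**1. Precision of the baseline difference.** Half-width of the 95% interval = t(0.975; 2n − 2) × √(2/n), in SD units.
- n = 12: 2.074 × 0.408 = 0.85 SD
- n = 10: 2.101 × 0.447 = 0.94 SD

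Even an observed difference of exactly zero would leave differences up to about 0.85 SD either way within the interval.

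**2. Chance imbalance under sound randomisation.** The difference in means has standard error √(2/n) SD, so P(|difference| > 0.5 SD) = 2 × [1 − Φ(0.5 / √(2/n))].
- n = 12: 0.5 / 0.408 = 1.225, giving 22%
- n = 10: 0.5 / 0.447 = 1.118, giving 26%

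**3. How often the t-test misses such an imbalance.** The test rejects in 5% of trials, and simulation shows that almost all of those rejections have an imbalance above 0.5 SD. The share of such imbalances that is non-significant is therefore about 1 − 0.05/P.
- n = 12: 1 − 0.05/0.221 = 77%
- n = 10: 1 − 0.05/0.264 = 81%

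Direct simulation (2,000,000 trials) gives 77% and 81%. Over all trials, an imbalance above 0.5 SD coexists with a non-significant test in about 0.22 × 0.77 = 17% (n = 12) or 0.26 × 0.81 = 21% (n = 10).

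**4. Would a proper equivalence test rescue the aim?** Two one-sided 5% t-tests, true difference zero, power by simulation:

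| Assumed margin | 10 per order | 12 per order |
|---|---|---|
| 0.5 SD | 0.1% | 0.2% |
| 0.8 SD | 12% | 22% |
| 1.0 SD | 39% | 54% |
| 1.5 SD | 89% | 94% |

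For 80% power, n per group = 2 × [(1.645 + 1.282)/margin]², which is 69 for a 0.5 SD margin and 27 for 0.8 SD. This trial could show equivalence only within margins too wide to be of interest.

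**5. Classifier, as an illustration.** The plan gives no success criterion. Suppose success means beating 50% accuracy at one-sided 0.05, with each child's prediction treated as independent.
- 24 children: at least 17 correct needed (71%; exact P = 0.032)
- 20 children: at least 15 correct needed (75%; exact P = 0.021)

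The best accuracy obtainable from one normal feature that differs by 0.8 SD is Φ(0.4) = 66%. A classifier with true accuracy 65% would miss the threshold 64% of the time (24 children) or 75% (20 children). At an observed accuracy of exactly 50%, the 95% interval is 29% to 71% or 27% to 73%. Section 4.7 lets children continue without EEG, so the number classified may be lower still.

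**The case against.** Several points on the other side have force.

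- **No rule is written down.** No sentence says that a non-significant result means equivalence, and no later analysis depends on the baseline result. A reader might infer a stated decision rule that produces a wrong conclusion. The documents support less: a stated purpose, with non-significance as the only route the text leaves to it.
- **The treatment comparison is largely protected.** It applies an unpaired t-test to within-subject differences, in which stable differences between the order groups largely cancel. A reader might infer that the primary result is invalid. That does not follow.
- **Power at a true difference is the wrong measure.** The t-test has 21.6% power (12 per order) or 18.5% (10) at a true 0.5 SD difference, and a reader might infer that equivalence will be wrongly declared about 80% of the time. Under sound randomisation there is no true difference. The 77% to 81% applies only to the 22% to 26% of trials with a realised imbalance that large.
- **Allocation may not be left intact.** Table 2 puts randomisation and desensitisation together in weeks 1 to 3, before the week-4 baseline, while the listed timeline puts randomisation after the baseline assessments. Replacements take the order of the child who left. If exclusions follow allocation, some look at baseline by order is sensible. This stands as a reason for description, but a t-test on 24 children does not settle it.
- **The classifier may be better specified elsewhere.** Multiplying 19 sensors × 6 bands × 11 measures gives 1,254 features, and a reader might infer that the classifier is meaningless whatever the truth. The plan does not say that all features enter one model, and it refers to a cited paper for the method. The weaker point stands: with at most 24 children, failing to separate the groups does not demonstrate equivalence.
- **Carryover.** Step 1 in section 6.1 calls the baseline analysis a carryover check, although the first baseline precedes any stimulation. That is a separate defect and adds nothing to the size of this one.

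**Conclusion.** The point holds as an error in what the analysis is said to establish. Difference tests and classifiers without a margin or criterion are aimed at an equivalence conclusion that about 12 children per order cannot support. The conclusion is the same at 10 or 12 per order, and for any assumed equivalence margin up to about 1.2 SD, where power at 12 per order is still only 77%.

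The result rests on two-sided 5% tests, normal data, 1:1 allocation, and the choice of 0.5 SD as a reference imbalance. The confidence-interval half-widths do not depend on that last choice.

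The consequence is an unsupported statement about the groups. A biased treatment estimate has not been shown. The point is worth correcting because the correction is nearly free.

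**What to change.** In section 6.1:
- Delete the baseline t-tests on BRIEF and PDDBI and the EEG classifier step.
- Remove the wording that says these analyses ensure, establish or demonstrate equivalence.
- Report first-baseline BRIEF, PDDBI and EEG features by order group as means, SDs and standardised differences with confidence intervals, without p-values.

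If the investigators want an equivalence claim, they would need to prespecify a margin and accept that this sample cannot meet a tight one.

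Any baseline adjustment of the treatment analysis should be decided and prespecified separately. It changes the model, and the week-12 baseline follows the first treatment period and may contain carryover, so it should not be treated like the week-4 baseline.

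The cost is a few sentences in section 6.1. Summary statistics are already planned, no new data are needed, and the analysis work falls slightly.
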